7.5.14 Germline DNA Measurements

CCI

Details regarding the preparation, handling, and shipping of samples are provided in the Study Manual.

7.5.14.1 Tumor Biomarkers Assessment

CCI

7.5.15 Concomitant Medications and Procedures

Concomitant medications and therapy will be recorded as specified in the [Schedule of Events](#). See Section 6.7 for a list of prohibited concomitant medications and therapies and Section 6.8 for a list of allowed concomitant medications and therapies.

7.5.16 Adverse Events

Monitoring of AEs, both nonserious and serious, will be conducted throughout the study as specified in the [Schedule of Events](#). See Section 10.1 for details regarding definitions, documentation, and reporting of pretreatment events, AEs, and SAEs.

7.5.17 Follow-Up Assessments (PFS and OS)

Patients who do not develop PD will continue to have PFS follow-up visits. The hematologic PFS follow-up should occur every 6 weeks from the EOT until the occurrence of progression or the start of subsequent antineoplastic therapy. A bone marrow aspirate and biopsy may be repeated at the discretion of the investigator as clinically indicated, but is not required during this follow-up period. The amyloid-organ PFS follow-up assessments should occur every 6 months from the EOT until the occurrence of progression (including hematologic progression) or the start of subsequent antineoplastic therapy. Refer to the [Schedule of Events](#) and Section 7.5.12 for appropriate assessments.

After the occurrence of PD or the initiation of subsequent antineoplastic therapy, patients will continue to have OS follow-up visits. The OS follow-up visits should be conducted every 12 weeks after documented PD or until the initiation of subsequent antineoplastic therapy. Data may be collected by methods that include, but are not limited to, telephone, e-mail, mail, and social security indexes. The duration of follow-up for OS will be 60 months after the last patient starts treatment.

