The estimated safe starting dose of MLN9708 will be selected from the dose-escalation portion of

the C16004 study, a phase 1 study of weekly dosing in patients with relapsed and refractory multiple myeloma. The starting dose will be at least 1 dose level below the C16004 MTD (if it has been reached by the time this study starts) and, if not, then a dose level completed without documented dose-limiting toxicity (DLT).

DLTs will be assessed in Cycle 1 only. In the context of emerging clinical data of single-agent MLN9708, dose-escalation of MLN9708 will continue until the MTD has been identified or a maximum planned dose (MPD) is determined to be safe.

Once the MTD/RP2D has been established, 2 expansion cohorts of patients with relapsed or refractory amyloidosis, including approximately 10 proteasome inhibitor-naïve patients and approximately 16 proteasome inhibitor-exposed patients, will be treated at the MTD/RP2D to more fully characterize the safety, tolerability, and efficacy of MLN9708, and the PK and pharmacodynamics of MLN9708 in this patient population. As many as 30 patients will be enrolled in the dose-escalation portion of the study, and as many as 20 additional patients (26 in total, including 6 patients from the dose-escalation portion) will be enrolled in the expansion cohorts.

Toxicity will be evaluated according to the investigators' documentation of adverse events (AEs) using the National Cancer Institute Common Terminology Criteria for Adverse Events, version 4.03. AEs will be assessed, and laboratory values, vital signs, and ECGs will be obtained to evaluate the safety and tolerability of MLN9708.

Patients will be evaluated at scheduled visits over 4 study periods: Screening, Treatment, End of Treatment (EOT), and Follow-up (progression-free and overall survival). Patients will discontinue treatment if they experience PD or unacceptable toxicity. The maximum duration of treatment with either single-agent MLN9708 or MLN9708 plus dexamethasone, however, will be 12 cycles unless after discussion between the investigator and the sponsor, it is determined that a patient would derive benefit from continued therapy beyond 12 cycles.

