The primary determinant of response for the purpose of continuing treatment is the hematologic response. Response will be determined according to standardized criteria. Hematologic response assessments are conducted after every cycle during treatment, at the end of treatment visit, and then every 6 weeks thereafter until disease progression or initiation of subsequent antineoplastic therapy. A bone marrow aspirate and biopsy are to be obtained at the Screening visit and may be repeated at the discretion of the investigator as clinically indicated and if CR is documented by other parameters in the standardized criteria.

Amyloid-related organ assessments are to be performed for all patients at screening; after Cycles 3, 6, 9, and 12; every 6 months thereafter until disease progression or the initiation of subsequent antineoplastic therapy; and at the End-of-Treatment visit. An evaluation of disease response according to standardized criteria will be performed at regular predefined intervals during treatment and then at regular intervals during follow up. Radiological evaluations (skeletal surveys, chest X-rays, computed tomography [CT] scan, or magnetic resonance imaging [MRI]), echocardiograms, blood samples and 24-hour urine collections (M-protein quantification, serum free light chain assay, immunofixation of serum and urine, quantification of immunoglobulins, serum cardiac markers) and bone marrow biopsy and aspirates will be employed to assess the status of the patient's disease response.

Quality of life (QOL) will be assessed only for patients in the expansion cohorts using the European Organization for Research and Treatment of Cancer QLQ-C30 (EORTC-QLQ-C30).

A blood sample will be collected for preparation of genomic deoxyribonucleic acid that will be used, as needed, to assess potential relationships **CC1** [REDACTED], clinical response, and safety.

Electrocardiograms will be acquired on Day 1 of Cycles 1 through 12 and at EOT and a 24-hour Holter monitor will be used at screening.

[figure not shown]
Study Population:

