Radiological evaluations and serial blood/urine samples will be employed to assess the status of the patient's amyloidosis. An evaluation of disease response using standardized criteria ^(53, 54) will be performed after each cycle during treatment and then at regular intervals during follow-up.

If patients are removed from treatment for unacceptable toxicity or reasons other than PD, they will continue in PFS follow-up until documented disease progression or the initiation of subsequent antineoplastic therapy. Once a patient experiences PD or starts subsequent antineoplastic therapy, they will proceed to the OS follow-up phase.

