7.5.12 Disease Assessments

7.5.12.1 Hematologic Disease Assessments

The primary determinant of response for the purpose of continuing treatment is the hematologic response. Response will be determined according to standardized criteria using a central laboratory. A bone marrow aspirate and biopsy are to be obtained at the Screening visit and may be repeated at the discretion of the investigator as clinically indicated and at the EOT. Immunohistochemistry of dominant clonal plasma cells is recommended. The response assessment is to be done during the rest cycle period (Days 22 through 28)

Quantitative Immunoglobulins, Serum M-protein, Urine M-protein, and Serum Free Light Chains

Serum specimens will be analyzed for quantitative immunoglobulins at screening, and if abnormal at screening, this test is to be repeated during Days 22 through 28 of each treatment cycle, and at the EOT visit. If the patient comes off treatment, but has not yet progressed it should be conducted every 6 weeks until disease progression.

Analysis for serum and urine M-protein and immunofixation is to be performed at screening, during Days 22 through 28 of each treatment cycle, and at the EOT visit. If the patient comes off treatment, but has not yet progressed it should be conducted every 6 weeks until disease progression.

Serum free light chain assay and ratio is to be performed at screening, during Days 22 through 28 of each treatment cycle, and at the EOT visit. If the patient comes off treatment, but has not yet progressed it should be conducted every 6 weeks until disease progression. The definition of hematologic response to treatment is based on the difference between the concentration of amyloid forming (involved) and uninvolved free light chain (dFLC). To be measurable dFLC must be at least 50 mg/L. Patients with dFLC < 50 mg/L are eligible for clinical studies but are evaluable only for complete remission. ^(55, 56)

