- If the patient starts an alternative antineoplastic therapy before the documentation of PD, then he or she will be censored at the date of the last available response assessment before the alternative antineoplastic therapy.

MLN9708**Study C16007 Statistical Analysis Plan**

- If the patient has no documented PD and has not started alternative antineoplastic therapy and is still alive at the time of analysis, he or she will be censored at the date of the last available response assessment.
- If the patient died before the documentation of PD and had not started any alternative antineoplastic therapy, he or she will be censored at the date of the last available response assessment.

Hematologic disease PFS is defined as the time from the date of the first dose of MLN9708 to the date of documented hematologic PD or any death. Organ disease PFS is defined as the time from the date of the first dose of MLN9708 to the date of documented organ PD or any death. Patients will be censored in any of the following scenarios:

- If the patient starts an alternative antineoplastic therapy before the documentation of PD, then he or she will be censored at the date of the last available response assessment prior to the alternative antineoplastic therapy.
- If the patient has no documented PD and has not started alternative antineoplastic therapy and is still alive at the time of analysis, he or she will be censored at the date of the last available response assessment.

OS is defined as the time from the date of the first dose of MLN9708 to the date of death. Patients without documentation of death at the time of analysis will be censored at the date last known to be alive. One-year OS rate is defined as the patient survival rate at 1 year after the date of the first dose of MLN9708.

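### Organ assessments end at hematologic progression (and, on the natural reading, the reverse), yet the SAP defines organ and hematologic PFS separately with no rule for follow-up ended by the other kind of progression

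*Protocol*

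**What the plan says.** **When assessments end (Protocol).** Section 7.5.17 sets organ follow-up at intervals of "6 months from the EOT until the occurrence of progression (including hematologic progression) or the start of subsequent antineoplastic therapy". Its hematologic sentence does not say which kind of progression is meant: "The hematologic PFS follow-up should occur every 6 weeks from the EOT until the occurrence of progression or the start of subsequent antineoplastic therapy". Section 7.5.12.1 is similar: for a patient off treatment who "has not yet progressed it should be conducted every 6 weeks until disease progression". Section 4.1 is general: "Once a patient experiences PD or starts subsequent antineoplastic therapy, they will proceed to the OS follow-up phase". Schedule of Events footnotes e and f agree. PFS visits run from the End-of-Treatment (EOT) visit to PD or new therapy. After that there is only 12-weekly survival contact, which may be by telephone or mail.

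On treatment, the Protocol Summary states: "Patients will discontinue treatment if they experience PD or unacceptable toxicity". It keeps one more organ assessment, since organ tests are due "every 6 months thereafter until disease progression or the initiation of subsequent antineoplastic therapy; and at the End-of-Treatment visit".

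**What is analysed (SAP).** Section 5.8.1 defines two of each endpoint. Organ PFS runs from "the first dose of MLN9708 to the date of documented organ PD or any death", and hematologic PFS is the mirror image. PFS is censored at the last assessment before alternative therapy, or at the last assessment if the patient is alive without PD in that domain. Time to progression and duration of response also censor deaths. No rule mentions PD in the other domain.

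SAP 5.8.2 names Kaplan-Meier for the hematologic endpoints and OS, and puts organ PFS and time to organ PD in a by-patient listing. Protocol 8.1.6 allows Kaplan-Meier for PFS and time to progression generally.

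**The concern.** A domain-specific PFS needs that domain to be observed until it progresses, the patient dies, or censoring occurs for a reason unrelated to its risk. Here observation of organs stops at hematologic PD. The protocol's background says that light chains cause the organ damage and that reducing the clone allows organs to improve. Organ follow-up therefore stops when organ risk has plausibly risen.

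After that point the SAP treats patients differently according to something that happens later. Those who die without new therapy become events at the date of death. Those who live are sent back to their last assessment. Kaplan-Meier assumes that leaving the risk set carries no information about the outcome, and this rule breaks that assumption. For time to progression and duration of response, where deaths are censored, the problem is potentially informative censoring only.

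At stake is what a reported organ or hematologic PFS means. Part of it would be time when nobody was looking.

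**Working it through.** **Plan's own figures.** The documents give no PFS or time-to-progression rate. The only design probabilities are for organ response, and they reproduce: at least 2 of 8 at 35% is 1 - 0.65^8 - 8(0.35)(0.65^7) = 0.831 (stated 83%), and at least 2 of 14 at 20% is 1 - 0.8^14 - 14(0.2)(0.8^13) = 0.802 (stated 80%). They do not bear on this point.

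**Step 1: two patients under the written rules.** Both have hematologic PD at month 4 on treatment, no organ PD seen and no new therapy. The EOT visit, at least 30 days after the last dose, gives a last organ assessment near month 5.
- Patient A dies at month 20: organ PFS event at 20 months, of which about 20 - 5 = 15 months were unobserved.
- Patient B is alive at analysis: censored at about month 5.

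Their organ follow-up was identical. Only later vital status separates them.

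**Step 2: which way this pushes PFS.**
- Longer: an organ PD between months 5 and 20 is missed and replaced by the later death.
- Longer: if the two kinds of progression are positively correlated, censoring at the first removes patients at higher risk.
- Shorter: survivors like B leave the risk set at month 5, while those like A stay in it until they die. Each death at time t_j is divided by too small a number n_j in S(t) = product of (1 - d_j/n_j).

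The net sign depends on rates and length of follow-up.

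**Step 3: size, by simulation (200,000 patients per scenario).**

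From the documents:
- hematologic tests every 28 days, then every 6 weeks;
- organ tests after Cycles 3, 6, 9 and 12, then every 6 months;
- the EOT assessment and the SAP censoring rules.

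Assumed, because the documents give nothing:
- either PD stops both domains;
- median time to hematologic/organ progression 9/18 or 15/15 months, correlation 0 or 0.5;
- median survival after first progression 12 or 36 months, and median 60 months for death without progression;
- 0%, 50% or 90% start new therapy 1.5 months after first PD;
- follow-up of 12-36 months (CSR cutoff) or 60-84 months (end of study).

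The comparison keeps assessing each domain to its own PD, new therapy or death, with the same censoring rules.

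18-month PFS in selected scenarios (survival after first PD, median 36 months):

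| Endpoint, cutoff | Medians, correlation | New therapy | As planned | Continued | Difference |
|---|---|---|---|---|---|
| Organ, end of study | 9/18, 0.5 | 0% | 0.52 | 0.40 | +0.12 |
| Organ, end of study | 9/18, 0.5 | 50% | 0.51 | 0.44 | +0.07 |
| Organ, end of study | 9/18, 0.5 | 90% | 0.49 | 0.49 | 0.00 |
| Organ, CSR | 9/18, 0 | 0% | 0.33 | 0.39 | -0.06 |
| Hematologic, end of study | 15/15, 0.5 | 0% | 0.42 | 0.34 | +0.08 |
| Hematologic, CSR | 15/15, 0.5 | 0% | 0.37 | 0.34 | +0.03 |

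Over all scenarios:
- organ: about -0.06 to +0.03 (CSR) and 0 to +0.12 (end of study);
- hematologic: about -0.01 to +0.03 (CSR) and 0 to +0.08 (end of study);
- with 90% starting new therapy: about 0.02 or less;
- second-domain progressions undocumented: about 75-96% of those before death and cutoff, or 48-95% counting only those before new therapy.

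If the comparison also follows patients past new therapy without censoring, organ PFS at the CSR cutoff is off by about -0.06 to +0.09.

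**The case against.** Several stronger readings are tempting, and the documents do not support them.

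- **That all assessments stop at either progression.** This is explicit only for organ assessments after hematologic PD. The reverse rests on the unqualified PD in 4.1 and the footnotes. Section 7.9 lists PD and hematologic marker progression as separate items, so the term is ambiguous. The symmetric reading is the natural one, but it is inferred, and the EOT assessment remains in any case.
- **That every endpoint runs on to death.** Time to progression and duration of response censor deaths, and PFS is censored once new therapy starts.
- **That both PFS endpoints come out too long.** The simulation gives both signs at the CSR cutoff. Too long is the usual result only with long follow-up and little new therapy.
- **That a biased organ PFS curve will be published.** The SAP plans only a listing for organ PFS. The listed values are affected, and Protocol 8.1.6 leaves Kaplan-Meier open.

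It is also fair to say that these are secondary endpoints in an uncontrolled phase 1 study with no formal tests, and that patients who progress may often start new therapy, where the effect nearly vanishes. All of this stands, and it limits size and severity. It does not supply the missing rule: patients A and B are still handled differently on identical observation.

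**Conclusion.** The concern holds in a limited form. The schedule observes time to the first progression of either kind, while the SAP reports each kind separately and is silent on follow-up ended by the other. For PFS this gives a bias whose direction cannot be stated in advance. For time to progression and duration of response it gives potentially informative censoring.

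The sizes above rest wholly on assumed rates and, for the hematologic endpoints, on the inferred symmetric stop rule. The qualitative result, that most second-domain progressions are not documented, held under nearly all assumptions tried. Long follow-up matters in practice: OS follow-up runs 60 months after the last patient, and SAP section 5 allows later updates or an end-of-study analysis. Severity is low to moderate. The primary safety and MTD/RP2D conclusions are untouched.

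**What to change.** 1. **SAP 5.8.1:** add a composite PFS, the time from first dose to the first of hematologic PD, organ PD or death. This is the PFS that the schedule observes, and it fits the unqualified PFS objective in the Protocol Summary and SAP 1.2.2. Report it beside the domain-specific PFS that Protocol 2.2 and 3.2 require.
2. **SAP 5.8.1 and 5.8.2:** for the domain-specific endpoints, treat first PD in the other domain as a competing event and report cumulative incidence. Do not count a death as a PFS event in a domain whose assessments had already ended.
3. **Protocol:** reconcile 4.1, 7.5.12.1, 7.5.17 and Schedule footnotes e and f on whether progression means either kind. Removing the parenthesis about hematologic progression from 7.5.17 would not be enough alone, because 4.1 and footnote e would still end disease assessments at PD.

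Items 1 and 2 use data already collected and cost some SAP wording and derivation. The reported PFS will probably be shorter, since the composite cannot exceed either of its parts. If the sponsor instead chose to continue each domain's visits to its own PD, the cost would be further organ visits every 6 months and hematologic visits every 6 weeks.

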7.6 Study Compliance

Study drug will be administered or dispensed only to eligible patients under the supervision of the investigator or identified sub-investigator(s). The appropriate study personnel will maintain records of study drug receipt and dispensing.

7.7 Completion of Treatment

Patients will be considered to have completed study treatment if they meet any of the following criteria:

- Have received at least 6 cycles of treatment
- PD after at least 28 days of Cycle 1

7.8 Completion of Study

Patients will be considered to have completed the study if they complete treatment according to the criteria outlined in Section 7.7 and complete 6 months of follow up (after the last dose of MLN9708).

7.9 Discontinuation of Treatment With Study Drug, and Patient Replacement

For patients who did not complete treatment by meeting 1 or more of the criteria outlined above, treatment may be discontinued permanently if any of the following criteria are met:

- AE
- Protocol violation
- Study terminated by sponsor
- Withdrawal by patient
- Lost to follow-up
- PD
- Initiation of subsequent therapies
- Progression of amyloid markers (hematologic), see Section 15.9.
- Clinically important decrease in ECOG performance status with organ function deterioration

- Other

At the time of study drug discontinuation, all study procedures outlined for the EOT visit will be completed. The primary reason for study drug discontinuation will be recorded on the electronic case report form (eCRF). Patients who do not meet the DLT-evaluable criteria in the dose-escalation part of the study may be replaced. See Section 8.1.3 for definitions of patient populations of the study.

Patients who are withdrawn from treatment during Cycle 1 for reasons other than DLT may be replaced.

7.10 Withdrawal of Patients From Study

A patient may also be withdrawn from the study for any of the following reasons:

- Study terminated by sponsor
- Initiation of subsequent therapies
- Withdrawal by patient
- Lost to follow-up
- Death
- Other

The consequence of study withdrawal is that no new information will be collected from that patient and added to the existing data or any database. However, every effort will be made to follow all patients for safety.

8. STATISTICAL AND QUANTITATIVE ANALYSES

8.1 Statistical Methods

8.1.1 Determination of Sample Size

A 3 + 3 dose-escalation scheme will be conducted, with 3 to 6 DLT-evaluable patients evaluated at each dose level. It is expected that as many as 30 patients will be enrolled in the dose-escalation part of this study.

Once the MTD/R2PD has been established, the following 2 expansion cohorts will be treated at the MTD or RP2D.

1. Proteasome inhibitor-naive expansion cohort including approximately 8 organ response-evaluable patients. There will be approximately 83% probability of observing at least 2 patients with organ responses among 8 patients based on the binomial probability calculation if the overall organ response rate is 35% for this population. Approximately 10 patients will be enrolled to obtain 8 response-evaluable patients.
2. Proteasome inhibitor-exposed expansion cohort including approximately 14 organ response-evaluable patients. There will be approximately 80% probability of observing at least 2 patients with organ responses among 14 patients based on the binomial probability calculation if the overall organ response rate is 20% for this population. Approximately 16 patients will be enrolled to obtain 14 organ response-evaluable patients.

Because approximately 6 patients in the dose-escalation part of the study will be included in the expansion cohorts, approximately 20 patients will be enrolled in the expansion part of this study.

Overall, as many as 50 patients will be enrolled in this study.

